Study Protocol

A comparison of pain perception using topical EMLA cream versus lidocaine injection for vulvar biopsy: a randomized controlled trial

NCT03654417

Study Protocol approved September 23, 2019

Research Abstract

The purpose of this study is to compare pain control during vulvar biopsy following either (1) application of EMLA (a eutectic mixture of local anesthetics lidocaine 2.5% and prilocaine 2.5%) cream or (2) injection of 1% lidocaine.

Subjects recruited from the Duke Gynecology Oncology clinic and the Duke Womens Cancer Care Raleigh clinic who will be receiving a vulvar biopsy will be randomized to receive either EMLA cream or injectable lidocaine in preparation for the biopsy. Subjects will complete a baseline survey, and sociodemographic information will be collected. Pain will be assessed using a 100 mm visual analog scale: at baseline, after application of EMLA or lidocaine injection, and immediately after vulvar biopsy. Subjects will then complete an exit survey on their perception of the tolerability and acceptability of the procedures. The primary outcome is highest subjective pain score. We hypothesize that lidocaine will provide better biopsy analgesia, but the benefit will be offset by the pain of lidocaine injection compared to EMLA application, thus there will not be a significant difference in highest pain scores between the two groups. Subjects will be compensated \$20 for their participation.

We chose a 16-mm difference on a standard 100-mm visual analog pain scale as value of clinical significance. In order to detect at least a 16-mm difference with 90% power and alpha of .05, we estimated a total sample size of 53. Highest mean pain scores between anesthetic methods will be compared as the primary outcome using T-test vs Wilcoxon Rank sum test. Patient perception of tolerability and acceptability of the procedure as well as the provider's satisfaction with the procedure will also be analyzed. There are no additional risks/benefits to the study participant for being part of the study as both methods of anesthesia are considered standards of care.

Primary Objectives

To compare highest subjective pain score with application of EMLA cream versus injection of lidocaine for analgesia for vulvar biopsy.

Secondary Objectives

To compare pain scores at vulvar biopsy

To investigate possible pathologic changes associated with EMLA cream administration

Purpose

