There is a small risk of topical reaction to the EMLA cream. If irritation does occur, the area of irritation will be cleansed with water and the procedure will be postponed until the irritation is resolved. The subjects will return to clinic to assess for resolution of the area and their indicated vulvar biopsy.

Costs to the Subject

No additional costs will be incurred by the participant as a result of participating in this study

Data Analysis and Statistical Considerations

A 16-mm difference on a standard 100-mm visual analog pain scale was deemed clinically significant. In order to detect a 16-mm difference with 90% power at an alpha level of 0.05 assuming a standard deviation of 25-mm, we estimated a needed sample size of 53 participants in each treatment arm. However, due to time limitations, data collection will end on March 12, 2019. Only patients consented on or prior to March 12, 2019 will be included in the study. Data will be recorded using Research Electronic Data Capture (REDCap), and the database will be locked on March 13, 2019. Pain will be measured during the application of EMLA cream or lidocaine injection, and immediately after biopsy. The primary outcome will be the highest pain score recorded during the procedure. The primary outcome sinclude pain score at vulvar biopsy, patient tolerability and acceptability, and provider's satisfaction with the procedure. All testing will be performed at a two-tailed significance level of 0.05.

If significance for the primary objective is not achieved, then patient accrual will continue based on a new sample size determined by the primary results of this analysis. This will be the number of new patients that need to be enrolled. Outcomes will be assessed again at the point when the final sample size is achieved.

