# Analysis Objectives

1. Objective: Describe patient characteristics in the analysis cohort by treatment arm and overall

**Analysis:** Create a baseline table of patient characteristics by treatment arm and overall. Continuous variables will be summarized with mean (SD), median (25th percentile, 75th percentile), and range. Categorical variables will be reported as frequency and percent. This table can be used to check that randomization approximately distributed confounders equally between the two treatment arms. P values will not be provided.

**Conclusions:** All pre-procedure data are presented in Table 1.1. There was a total of 37 enrolled patients, with 19 and 18 in the EMLA cream and lidocaine injection group, respectively.

Table 1.1. Pat	ient demographics and cha	racteristics	
	EMLA cream Li	docaine injection only	Total
	(N=19)	(N=18)	(N=37)
Generalized Anxiety Disorder 7-Item 8	Scale: Over the last 2 weeks	, how often have you	been bothered
by	y the following problems?	-	
1. Feeling nervous, anxious, or on edge			
Not at all sure	8 (42.1%)	10 (55.6%)	18 (48.6%)
Several days	7 (36.8%)	5 (27.8%)	12 (32.4%)
Over half the days	2 (10.5%)	1 (5.6%)	3 (8.1%)
Nearly every day	2 (10.5%)	2 (11.1%)	4 (10.8%)
2. Not being able to stop or control wor	rrying		
Not at all sure	13 (68.4%)	13 (72.2%)	26 (70.3%)
Several days	5 (26.3%)	3 (16.7%)	8 (21.6%)
Nearly every day	1 (5.3%)	2 (11.1%)	3 (8.1%)

	EMLA cream Li (N=19)	idocaine injection only (N=18)	Total (N=37)
3. Worrying too much about different things			( )
Not at all sure	13 (68.4%)	7 (38.9%)	20 (54.1%)
Several days	3 (15.8%)	7 (38.9%)	10 (27.0%)
Over half the days	1 (5.3%)	2 (11.1%)	3 (8.1%)
Nearly every day	2 (10.5%)	2 (11.1%)	4 (10.8%)
4. Trouble relaxing			
Not at all sure	13 (68.4%)	6 (33.3%)	19 (51.4%)
Several days	4 (21.1%)	8 (44.4%)	12 (32.4%)
Over half the days	1 (5.3%)	1 (5.6%)	2 (5.4%)
Nearly every day	1 (5.3%)	3 (16.7%)	4 (10.8%)
5. Being so restless that it's hard to sit still			
Not at all sure	16 (84.2%)	12 (66.7%)	28 (75.7%)
Several days	1 (5.3%)	4 (22.2%)	5 (13.5%)
Over half the days	1 (5.3%)	1 (5.6%)	2 (5.4%)
Nearly every day	1 (5.3%)	1 (5.6%)	2 (5.4%)
6. Becoming easily annoyed or irritable			
Not at all sure	14 (73.7%)	9 (50.0%)	23 (62.2%)
Several days	5 (26.3%)	8 (44.4%)	13 (35.1%)
Nearly every day	0 (0.0%)	1 (5.6%)	1 (2.7%)
7. Feeling afraid as if something awful might			
happen			
Missing	1 (.%)	0 (.%)	1
Not at all sure	14 (77.8%)	14 (77.8%)	28 (77.8%)

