# Table 1.1. Patient demographics and characteristics

2. Objective: Compare highest subjective pain score between patients receiving EMLA cream vs. lidocaine

**Analysis:** Linear regression will be used to test if the highest pain score differs between treatment arms, controlling for baseline pain. The regression coefficient, 95% confidence interval, and p value will be reported for the treatment effect. A significant p value would indicate that the highest pain score, on average, differed between the two treatment arms. If there is not a significant difference between treatment arms with regards to the highest pain score, then the mean and variance estimates from these patients will be used to recalculate the sample size needed (objective 3).

**Conclusions:** The highest pain score was created as the maximum between pain during application of anesthesia and pain immediately following biopsy. The median highest pain score in the EMLA cream group was 20.0 mm vs. 56.5 mm in the lidocaine injection group.

Table 2.1. Highest pain score by treatment arm					
	EMLA cream (N=19)	Lidocaine injection only (N=18)	Total (N=37)		
Highest pain score (n	nm)				
Ν	19	18	37		
Mean (SD)	26.7 (29.0)	52.5 (32.0)	39.2 (32.8)		
Median	20.0	56.5	27.0		
Q1, Q3	5.0, 50.0	26.0, 80.0	12.0, 61.0		
Range	(0.0-100.0)	(5.0-100.0)	(0.0-100.0)		

All patients in the lidocaine injection group reported having the same as or more pain during the injection than the biopsy. Four out of nineteen patients in the EMLA cream group reported more pain from the application of the cream than the biopsy, and three reported the same amount of pain.

Frequency Row Percent	More pain from biopsy	Same amount of pain	More pain from application of anesthesia	Total
Lidocaine injection only	0 0.00	1 5.56	17 94.44	18
EMLA cream	12 63.16	3 15.79	4 21.05	19
Total	12	4	21	37

From the linear regression model, patients that received EMLA cream were expected to report their highest pain score 25.7 mm lower than the lidocaine injection group (95% CI = [-45.1, -6.3], p < 0.01). In other words, the highest pain score in the EMLA cream group was significantly lower than in the lidocaine injection group.

**3. Objective:** Calculate the new sample size needed using effect estimates from the interim analysis

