**Analysis:** Using the difference in means between groups and the estimate of the standard deviation, the sample size needed to detect the observed difference in pain scores between the two treatment arms at 90% power with an alpha level of 0.05 using a two-sample t-test will be calculated. This will be the number of patients that will need to be NEWLY accrued. The current patients do not count towards this sample size.

**Conclusions:** Since the highest pain score was significantly lower in the EMLA cream group compared to the lidocaine group, the trial does not need to continue.

4. Objective: Compare secondary and exploratory outcomes between treatment arms

**Analysis:** The secondary objective, pain at vulvar biopsy, will be compared between treatment arms using linear regression, controlling for baseline pain, similar to the primary objective. The exploratory objectives, excluding provider's response to "overall, how satisfied were you with the procedure," will be compared between treatment arms using Wilcoxon rank sum test. A significant p value would mean that one of the treatment arms tended to have higher scores on the VAS than the other. Since the same providers are rating their satisfaction with the procedure multiple times, the responses will be correlated. To take this into account, provider procedure satisfaction scores will be compared between treatment arms using generalized estimating equations (GEE) assuming a normal distribution. The working correlation matrix will be chosen using QIC and the robust variance estimator will be used.

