**Conclusions:** There was not a significant difference between treatment arms with regards to pain at biopsy (EMLA cream  $\beta$  = 6.9; 95% confidence interval [-12.0, 25.9]; p = 0.47). Patients that were randomized to EMLA cream had a significantly better experience with the procedure than those that received lidocaine (p = 0.02). There was not a significant difference between treatment arms for patient acceptability or provider's perception of subject tolerance (p = 0.06 for both). A compound symmetric working correlation structure was used for the marginal model comparing provider satisfaction scores between treatment groups. There was not a significant difference between treatment treatment arms for provider satisfaction scores (p = 0.35). As a note, do not place too much emphasis on the insignificant results as this is still a small sample size and the trial was not powered for these objectives. A lack of statistical significance does not prove that there is no difference. Summary statistics for the secondary and exploratory objectives are shown in table 4.1. A lower score indicates better results for all outcomes.

	EMLA cream L (N=19)	idocaine injection only (N=18)	Total (N=37)	P value
Pain at vulvar biopsy (mm)				0.47
Ν	19	18	37	
Mean (SD)	24.1 (30.3)	17.4 (29.1)	20.8 (29.5)	
Median	6.0	3.0	5.0	
Q1, Q3	1.0, 50.0	0.0, 15.0	0.0, 26.0	
Range	(0.0-100.0)	(0.0-100.0)	(0.0-100.0)	
Patient's experience with the procedure (lower is				0.02
better)				
Ν	19	18	37	
Mean (SD)	11.2 (23.1)	27.1 (29.7)	18.9 (27.3)	
Median	2.0	17.0	6.0	
Q1, Q3	0.0, 17.0	5.0, 38.0	0.0, 25.0	
Range	(0.0-99.0)	(0.0-100.0)	(0.0-100.0)	
Patient's acceptability of the procedure (lower				0.06
is better)				
Ν	19	18	37	
Mean (SD)	10.8 (21.1)	17.9 (19.8)	14.2 (20.5)	
Median	0.0	10.5	5.0	
Q1, Q3	0.0, 18.0	1.0, 33.0	0.0, 21.0	
Range	(0.0-86.0)	(0.0-67.0)	(0.0-86.0)	
Provider's perception of patient tolerance (lower is better)				0.06
Ν	19	18	37	
Mean (SD)	16.6 (28.7)	20.4 (18.0)	18.5 (23.8)	
Median	3.0	15.0	13.0	
Q1, Q3	0.0, 19.0	9.0, 27.0	0.0, 20.0	
Range	(0.0-99.0)	(0.0-62.0)	(0.0-99.0)	
Provider's satisfaction with the procedure (lower				0.35
is better)				
Ν	19	18	37	
Mean (SD)	21.2 (35.8)	13.1 (13.5)	17.2 (27.3)	
Median	3.0	9.5	7.0	
Q1, Q3	0.0, 18.0	3.0, 18.0	0.0, 18.0	
Range	(0.0-99.0)	(0.0-51.0)	(0.0-99.0)	

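### The reported primary CI and p < 0.01 carry no small-sample correction: least squares with t(34) gives about [-46.7, -4.7] mm and p about 0.018.

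*SAP*

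**What the plan says.** SAP Objective 2 sets the primary analysis: "Linear regression will be used to test if the highest pain score differs between treatment arms, controlling for baseline pain". The analysis set is 37 patients, "with 19 and 18 in the EMLA cream and lidocaine injection group, respectively". The result is given as "25.7 mm lower than the lidocaine injection group (95% CI = [-45.1, -6.3], p < 0.01".

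Objective 4 uses the same model for pain at biopsy and reports an EMLA coefficient of 6.9 mm, "95% confidence interval [-12.0, 25.9]; p = 0.47".

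Neither objective names a variance estimator or a reference distribution for these two regressions. For provider satisfaction, by contrast, Objective 4 is explicit: "The working correlation matrix will be chosen using QIC and the robust variance estimator will be used".

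The protocol's Research Abstract names a different primary comparison: "Highest mean pain scores between anesthetic methods will be compared as the primary outcome using T-test vs Wilcoxon Rank sum test". Its Data Analysis section adds: "All testing will be performed at a two-tailed significance level of 0.05".

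**The concern.** Linear regression without further qualification is normally read as least squares, with the residual variance on n minus 3 degrees of freedom here and t critical values. The reported interval is narrower than that model can give from the SAP's summary tables. It is also narrower than the interval from an unadjusted two-sample t-test on Table 2.1. Baseline adjustment cannot account for the gain, because it moves the estimate by only 0.1 mm and removes almost no residual variance.

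This is the primary result, and Objective 3 uses its significance to conclude that accrual need not continue. If the interval rests on a large-sample approximation in 37 patients, its precision is overstated, the nominal error rate is not the two-sided 0.05 of the protocol, and p < 0.01 makes the evidence look stronger than it is.

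**Working it through.** **Inputs (EMLA n = 19, lidocaine n = 18)**

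| Quantity | EMLA mean (SD) | Lidocaine mean (SD) | Difference | Source |
|---|---|---|---|---|
| Highest pain, mm | 26.7 (29.0) | 52.5 (32.0) | -25.8 | Table 2.1 |
| Pain at biopsy, mm | 24.1 (30.3) | 17.4 (29.1) | 6.7 | Table 4.1 |
| Baseline vulvar pain, mm | 7.7 (21.4) | 2.4 (4.5) | 5.3 | Table 1.1 |

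The adjusted effects are -25.7 (primary) and 6.9 (biopsy pain), as reported.

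**Rebuilding the adjusted model (primary)**

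- Baseline slope = (unadjusted - adjusted difference) / baseline difference = (-25.8 + 25.7)/5.3 = -0.019.
- Within-arm sum of squares of the outcome = 18 × 29.0² + 17 × 32.0² = 32546.
- Within-arm sum of squares of baseline pain, Sxx = 18 × 21.4² + 17 × 4.5² = 8587.5.
- Residual sum of squares, RSS = 32546 - 0.019² × 8587.5 = 32543. As a check, the total SD of 32.8 gives 36 × 32.8² - 25.8² × 19 × 18/37 = 32578, which agrees within rounding.
- Variance factor = 1/19 + 1/18 + 5.3²/8587.5 = 0.1115.
- SE = √(RSS/divisor × 0.1115).

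**Reproducing the reported figure.** With divisor 37, SE = 9.90. With 1.96 the interval is -25.7 ± 19.4 = [-45.1, -6.3], p = 0.0094. This is the reported result to the decimal. The alternatives do not match:

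| Divisor | Quantile | SE | Half-width | 95% CI | p |
|---|---|---|---|---|---|
| 37 | normal | 9.90 | 19.4 | [-45.1, -6.3] | 0.0094 |
| 34 | t(34) | 10.33 | 21.0 | [-46.7, -4.7] | 0.018 |
| 34 | normal | 10.33 | 20.2 | [-45.9, -5.5] | 0.013 |
| 37 | t(34) | 9.90 | 20.1 | [-45.8, -5.6] | 0.014 |

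When every rounded input is varied within ±0.05, the t(34) half-width stays at 20.9 to 21.0 and p at 0.0175 to 0.0184, so rounding cannot produce 19.4.

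**Pain at biopsy.** The slope is (6.7 - 6.9)/5.3 = -0.038 and RSS = 30909. Divisor 37 with 1.96 gives [-12.0, 25.8], p = 0.475. Over input rounding the upper limit runs from 25.7 to 25.9, so this agrees with the report. Divisor 34 with t(34) gives SE 10.07, [-13.6, 27.4], p = 0.50.

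**Check from the reported line alone.** The reported half-width is 19.4. Read as a t(34) interval, it implies SE 9.55 and p = 0.0109 (0.0106 to 0.0113 over rounding), which contradicts p < 0.01. Read as a normal interval, it implies p = 0.0094, which agrees.

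**Could adjustment explain it?** For least squares with t(34) to reach a half-width of 19.4, RSS would have to fall to about 27798, which needs a slope of about ±0.74. The adjusted effect would then be about -29.7 or -21.9, not -25.7.

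**Unadjusted t-test on Table 2.1.** Pooled SD 30.49, SE 10.03, t(35) = -2.57, CI [-46.2, -5.4], p = 0.015. The Welch version also gives p = 0.015.

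**Robust variance.** This cannot be computed from summaries. In 5,000 constructed datasets with the published means and SDs (assumed normal residuals, one EMLA baseline value near 92), an uncorrected sandwich SE with 1.96 gave half-widths of 19.3 to 20.0 (primary) and 18.8 to 19.4 (biopsy pain), 5th to 95th percentile. Both reported widths fall inside those ranges.

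**Error rate.** Divisor 37 with 1.96 is equivalent to a t(34) critical value of 1.96 × √(34/37) = 1.879. Under normal errors with constant variance, that gives size 6.9% and coverage 93.1%. The same shortcut at nominal 0.01 has size about 1.9%.

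**The case against.** The reported line is internally consistent under a normal quantile, and a maximum-likelihood Wald interval is a recognised large-sample method. On that view nothing was miscalculated and the fault is an undeclared, slightly liberal method. This is fair as to cause: the SAP does not say how the model was fitted, and the attribution rests on a numerical match. It does not rescue the figures. A reader told only that linear regression was used will expect least squares with t(34), and neither candidate explanation includes a small-sample correction.

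The consequences are also limited. No decision in the documents depends on 0.01; the only test level is 0.05, and p of about 0.018 meets it. Both -6.3 and -4.7 mm fall well short of the 16 mm difference that the protocol calls clinically significant, and biopsy pain is non-significant either way. All of this stands, and it limits the point to how precision and strength of evidence are reported.

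Finally, the protocol also names the Wilcoxon test, whose p value cannot be computed from summaries. The finding is therefore that t-based inference, adjusted or unadjusted, does not support p < 0.01. It does not extend to every test the protocol mentions.

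**Conclusion.** The concern holds. For the regression as described, the primary result should read about -25.7 mm (95% CI -46.7 to -4.7), p about 0.018. The reported half-width of 19.4 mm is about 8% below the 21.0 mm expected, and the limit nearest zero moves by 1.6 mm. For biopsy pain the result should be about 6.9 mm (-13.6 to 27.4), p about 0.50.

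These values assume model-based least squares and the published summaries, with rounding allowed for. They are well determined because the implied baseline slope is close to zero. The size and coverage figures assume normal errors with constant variance. Division by 37 with a normal quantile is the best match to both results but remains an inference. The estimate, its direction, significance at two-sided 0.05 and the decision not to continue accrual are unaffected.

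**What to change.** Confirm from the analysis code which variance and reference distribution were used. Refit both models on the patient-level data with residual-df variance and t(34) critical values, and replace the intervals and p values in the conclusions of Objectives 2 and 4, with the biopsy-pain p value in Table 4.1. Add one sentence to the analysis text of both objectives naming the variance estimator and reference distribution. If a robust variance was used, say so and apply a small-sample correction; the corrected interval then depends on the patient-level data and may differ from the values above. Declaring the large-sample approximation would make the present figures reproducible but would leave the test too liberal at this sample size.

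The cost is two model reruns, the edited result lines and one added sentence. The figures become slightly less favourable, no new data are needed, and the conclusion at 0.05 stands.

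### Should the SAP's extension rule, which sizes on the observed interim difference instead of 16 mm, be rewritten?

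*SAP*

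**What the plan says.** Protocol, Data Analysis and Statistical Considerations, sets the target: "A 16-mm difference on a standard 100-mm visual analog pain scale was deemed clinically significant". From it, "assuming a standard deviation of 25-mm, we estimated a needed sample size of 53 participants in each treatment arm", with 90% power and two-sided 0.05. The same section ends recruitment early for lack of time and adds that, without significance on the primary objective, "patient accrual will continue based on a new sample size determined by the primary results of this analysis". It closes: "Outcomes will be assessed again at the point when the final sample size is achieved".

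SAP, Analysis Objectives, Objective 2 states the trigger, "If there is not a significant difference between treatment arms with regards to the highest pain score", in which case "the mean and variance estimates from these patients will be used to recalculate the sample size needed". Objective 3 then defines the new number as "the sample size needed to detect the observed difference in pain scores between the two treatment arms at 90% power", by a two-sample t-test at alpha 0.05, and adds: "The current patients do not count towards this sample size".

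The SAP also reports the outcome. Objective 2 finds a significant difference between arms, and the Objective 3 conclusion is that no further accrual is needed.

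**The concern.** A sample size is normally tied to the smallest difference worth detecting. Here the extension is tied to whatever 37 patients happened to show, and only when that was too small to be significant. Small observed differences give very large numbers, so chance would largely set the size, and the text supplied states no ceiling. (A small part of the SAP was not available for review, so a cap there cannot be excluded.)

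The sponsor's own hypothesis was that the arms would not differ significantly in highest pain, so this was the branch the plan expected to enter. The stake would have been an extension that could not be completed, or one chasing a difference below the sponsor's own threshold. The documents also leave open whether the second analysis would pool the first 37 patients.

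**Working it through.** **Inputs.** Target 16 mm, SD 25, 90% power, two-sided 0.05 (protocol). First look 19 EMLA and 18 lidocaine (SAP Objective 1). Highest pain, mean (SD): 26.7 (29.0) and 52.5 (32.0) (SAP Table 2.1). Difference 52.5 - 26.7 = 25.8 mm. Pooled SD = sqrt[(18 × 29.0² + 17 × 32.0²)/35] = 30.49.

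**The plan's own figure.** Normal approximation: n per arm = 2 × (1.960 + 1.282)² × 25²/16² = 51.3, so 52. The t-test gives 53, which agrees with the protocol's figure per arm. At SD 30.49 the t-test gives 78. Totals for 16 mm are therefore 106 and 156.

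**Where the rule bites.** With 19 and 18 patients, an unadjusted t-test is non-significant when the observed difference is below 2.030 × SD × sqrt(1/19 + 1/18) = 2.030 × SD × 0.3289. That is 16.7 mm at SD 25 and 20.4 mm at SD 30.49. At that limit Objective 3 asks for about 49 per arm. Below it the number climbs quickly: at SD 25, 133 per arm for an observed 10 mm and 527 for 5 mm.

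**Size of a triggered extension.** First looks were simulated (millions per setting, normal data, unadjusted t-test), the non-significant ones kept, and Objective 3 applied to the observed difference and SD. The true differences are scenarios. Entries are SD 25 / SD 30.5.

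| True difference | Chance of entering branch | Median total new patients | Multiple of size for 16 mm | Multiple of size for the true difference |
|---|---|---|---|---|
| 0 mm | 95% / 95% | 948 / 946 | 8.9 / 6.1 | not defined |
| 10 mm | 78% / 84% | 406 / 508 | 3.8 / 3.3 | 1.5 / 1.3 |
| 16 mm | 53% / 66% | 226 / 288 | 2.1 / 1.8 | 2.1 / 1.8 |
| 25.8 mm | 14% / 29% | 148 / 172 | 1.4 / 1.1 | 3.5 / 2.8 |

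The last column divides by twice the t-test n per arm for the true difference: 133 / 197 at 10 mm, 53 / 78 at 16 mm and 21 / 31 at 25.8 mm. At a true 16 mm the 5th to 95th percentile of the total runs from 104 to about 8,400 (SD 25) and from 106 to about 17,900 (SD 30.5).

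**The obvious alternative.** Keep 16 mm and update only the SD. At a true 16 mm:
- The 5th to 95th percentile narrows to 72-154 / 106-226 in total.
- Extensions smaller than 16 mm requires become more frequent: 45% / 47%, against 6% / 25% under the present rule.
- When the observed difference exceeds 16 mm without reaching significance, the extension grows by a median of 8 / 19 per arm (95th percentile 26 / 52).

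**Was the rule used?** The reported interval, -45.1 to -6.3, excludes zero. The unadjusted check agrees: 25.8/(30.49 × 0.3289) = 2.57 on 35 degrees of freedom, p = 0.015. The trigger was not met, and the SAP gives no extension size.

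**The case for a change.** The strongest case for a change is that the weakness is real and was foreseeable. Had the sponsor's hypothesis held with a true difference near zero, the branch would have been entered about 95% of the time, with a median near 950 new patients, in a study that had already stopped at 37 for lack of time. The rule can also undersize. At the trigger limit, 49 per arm has 88% power for 16 mm at SD 25 but only 73% at SD 30.5 if new patients alone are analysed (96% and 86% if the first 37 are pooled). A sentence in each document would tie the rule to 16 mm.

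All of that stands as criticism of the rule, with two limits. First, the large multiples depend on taking 16 mm as the only legitimate target. Measured against the size for the true difference, the median excess at 10 mm is only 1.3 to 1.5 times. The protocol lets the interim results set the new size, so the SAP does not contradict it. Second, the alternative trades occasional huge extensions for more frequent, usually modest, undersizing. It is a reasonable preference but not free. Neither the criticism nor the remedy reaches anything the trial did or reported.

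**Conclusion.** No change to the plan. Objective 3 is a weak way to size an extension, with a median about twice the 16 mm requirement at a true 16 mm, six to nine times at a true zero, and a very long upper tail. But it governs only a branch that the significant first look closed. The estimate of -25.7 mm, its interval and the decision to stop are the same whichever sizing rule is written. Editing the rule after the result is known would be a retrospective change with no gain. For a future trial, holding the target at 16 mm, re-estimating only the SD and stating whether first-look patients are pooled would be worth considering, with the undersizing cost above in view.

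The multiples assume normal data, an SD of 25 or 30.5 and an unadjusted trigger. The SAP's trigger adjusts for baseline pain. Scaling it to the reported interval half-width, (45.1 - 6.3)/2 = 19.4 mm against 20.36 mm, moves the medians at a true 16 mm only to 248 / 314. That the branch is closed rests on the SAP's reported result, not on these assumptions.

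### Provider satisfaction is tested by GEE with a robust variance and no stated small-sample correction, although the ratings come from an unstated number of providers smaller than 37 (minor; the conclusion does not change)

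*SAP*

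**What the plan says.** The Protocol, under Data Analysis and Statistical Considerations, sets one level for every test: "All testing will be performed at a two-tailed significance level of 0.05".

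The SAP, under Analysis Objectives, Objective 4, singles out provider satisfaction for a clustered analysis. The reason given is: "Since the same providers are rating their satisfaction with the procedure multiple times, the responses will be correlated". The method is that "provider procedure satisfaction scores will be compared between treatment arms using generalized estimating equations (GEE) assuming a normal distribution", and then: "The working correlation matrix will be chosen using QIC and the robust variance estimator will be used".

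The conclusions to Objective 4 report the structure chosen: "A compound symmetric working correlation structure was used for the marginal model comparing provider satisfaction scores between treatment groups". Table 4.1 gives mean (SD) satisfaction of 21.2 (35.8) for EMLA (N = 19) and 13.1 (13.5) for lidocaine (N = 18), with p = 0.35. No interval is printed for this outcome.

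The SAP lists provider perceptions under its Exploratory Objective, and the Objective 4 conclusions caution that the trial was not powered for these comparisons. Neither document gives the number of providers, the ratings per provider, a small-sample correction, or the test and reference distribution behind the p value.

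**The concern.** The robust (sandwich) variance is justified by a large number of independent clusters. Here the clusters are providers, and there must be fewer than 37 because some rated more than once. With few clusters the sandwich underestimates the sampling variance on average, and a normal reference ignores how noisy that variance estimate is. Both effects push a Wald test towards too many false positives.

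The SAP chose GEE in order to respect the clustering. At this sample size, without a small-sample correction, that choice does not deliver the Protocol's 5% level. What is at stake is the validity of one exploratory p value.

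**Working it through.** **Inputs from the documents.** 37 ratings, 19 EMLA and 18 lidocaine (SAP, Objective 1 and Table 4.1); Gaussian GEE with robust variance (SAP, Objective 4); compound symmetric, that is exchangeable, working correlation (Objective 4 conclusions); two-sided 0.05 (Protocol).

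**Assumptions, not in the documents.** Number of providers K, intra-provider correlation (ICC), workload per provider, and a Wald z test as the use made of the robust variance.

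**Step 1: the printed p value.** It cannot be reproduced exactly without provider identifiers. An unclustered comparison from Table 4.1 gives:

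- difference = 21.2 − 13.1 = 8.1
- SE = √(35.8²/19 + 13.5²/18) = √(67.46 + 10.13) = 8.81
- z = 8.1/8.81 = 0.92, two-sided p = 0.358

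On a normal reference, the printed 0.35 corresponds to |z| = 0.935, so an SE of 8.1/0.935 = 8.67. The two SEs are close.

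**Step 2: type I error of the test as specified.** Data were simulated with no treatment effect, 37 ratings split 19/18, patients of both arms within providers, and an exchangeable GEE with uncorrected sandwich. The null was rejected when |estimate/SE| > 1.96.

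| Providers assumed | Type I error, robust Wald z |
|---|---|
| 3 | 27-30% |
| 5 | 17-19% |
| 10 | 11-12% |
| 15-20 | 9-11% |

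A wider set of scenarios (ICC 0.05-0.30, even or uneven workload, equal or printed arm SDs, skewed 0-100 scores) gave 17-22% at 5 providers, 11-17% at 10 and 10-16% at 20. With 25-30 providers and even workload it was 9-10%. Each cell had 1,500 to 3,000 runs, with Monte Carlo error of about 0.5 to 1.2 percentage points.

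**Step 3: source of the excess.** The ratio of the mean robust SE to the true sampling SD of the estimate was 0.64-0.70 at 3 providers, 0.72-0.79 at 5 and 0.78-0.88 at 10.

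**Step 4: with a correction.** Mancl-DeRouen variance with t on K − 1 df gave about 2-6% across the provider counts tried. With t on K − 2 df it gave 0-2% at 3-4 providers, which is conservative, and about 3-6% at 8-20. Changing only the reference to t on K − 1, with the variance left uncorrected, still left about 7-13%.

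**Step 5: effect on the reported result.** Take |z| = 0.935 from Step 1. Column A refers it to t on K − 1 df. Column B, a rough harsher version, also divides it by √(K/(K − 2)) and uses K − 2 df.

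| Providers assumed | A | B |
|---|---|---|
| 3 | 0.45 | 0.68 |
| 5 | 0.40 | 0.52 |
| 10 | 0.37 | 0.43 |
| 20 | 0.36 | 0.39 |

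Every value is non-significant.

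**The case against.** **The test is not named.** The SAP specifies a variance estimator and no test statistic. The same robust variance can feed a generalised score test. In simulation that test gave 0% at 3 providers, about 2% at 5 and 3.5-5.5% at 10-15, so it is not inflated. This stands in part. A robust variance named for a treatment coefficient ordinarily means a Wald test, so the problem remains on the natural reading. Its size, however, depends on an unstated test as well as an unstated provider count, and both need reporting.

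**No conclusion is affected.** The outcome is exploratory, the result is non-significant, the SAP warns about power, and the error runs towards false positives where none was claimed. This stands, and it sets the weight of the point.

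**Stronger readings that the documents do not support.**

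- A reader might infer that the SE in this sample was too small. Step 1 does not show that: the SE implied by p = 0.35 (8.67) is close to the unclustered one (8.81). The simulated bias is an average over repeated samples.
- A reader might infer that the provider's tolerance rating (p = 0.06) would turn falsely significant under the same model. That p value is from a rank test, whereas a normal GEE compares means. From Table 4.1 the difference is 20.4 − 16.6 = 3.8, SE = √(28.7²/19 + 18.0²/18) = 7.83, z = 0.49 and p is about 0.63. Shrinking that SE by the worst ratio in Step 3 (0.64) still gives p of about 0.45.
- A reader might infer that a published confidence interval is too narrow. None is printed or planned for this outcome.
- A reader might infer that choosing the working correlation by QIC inflates the error further. The simulations fixed an exchangeable structure, so they say nothing about that step.

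**Conclusion.** The point holds as a minor one. As written, and read as a Wald z test, the analysis does not keep the Protocol's two-sided 5% level for provider satisfaction. Assuming 3 to 20 providers, type I error runs from about 27-30% down to about 9-11%. The direction did not depend on the provider count over the range tried; the size does, and it also rests on the absence of any correction, which is read from the SAP's silence. The reported p = 0.35 would rise somewhat under correction and remain non-significant, so neither the finding for this exploratory outcome nor the primary conclusion changes.

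**What to change.** In SAP Objective 4, replace the plain robust variance with a small-sample bias-corrected robust variance (for example Mancl-DeRouen) and a t reference on cluster-based degrees of freedom, providers minus 1. Specify an exchangeable working correlation in place of selection by QIC; this is the structure already used. Re-report the p value with the number of providers and the ratings per provider, and state which test and reference distribution produced the 0.35. Because results are already reported, label the new figure as a correction made after the analysis.

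The cost is a wording change and a software option on data already held. The downside is a larger p value, lower power, and some conservatism if there are very few providers.
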